# 8.3.4 Regulatory Reporting Requirements for Serious Adverse Events

Prompt notification by the Investigator to the Sponsor of a SAE is essential so that legal obligations and ethical responsibilities towards the safety of participants are met.

The Sponsor will comply with country-specific regulatory requirements relating to safety reporting to the regulatory authority, Institutional Review Boards (IRB)/Independent Ethics Committees (IEC), and investigators.

An Investigator who receives an investigator safety report describing a SAE or other specific safety information (e.g., summary or listing of SAEs) from the Sponsor will review and then, file it along with the Investigator's Brochure and will notify the IRB/IEC, if appropriate according to local requirements.

For immediate and expedited reporting requirements from Investigator to Sponsor and from Sponsor to Health Authority, investigators, IRB and EC, see Appendix 2.

### 8.3.4.1 Emergency Medical Contacts

This section does not apply to this study.

# 8.3.5 Non-Serious Adverse Events of Special Interest

This section does not apply to this study.

# 8.3.6 Disease-Related Events and/or Disease-Related Outcomes Not Qualifying as AEs or SAEs

This section does not apply to this study.

### 8.3.7 Management of Specific Adverse Events

This section does not apply to this study.

#### 8.4 BIOMARKERS

# 8.4.1 Digital Biomarkers

At the screening visit, the caregiver will be provided with a study smartphone and wrist-worn wearable with a pre-installed application (also called 'app'). The smartphone will be pre-configured to ensure that the pre-installed app will be accessible by the participant and caregiver, with other apps and settings inaccessible. The app will include a collection of digital biomarker assessments, including surveys and active tests, for the caregiver and participant to complete. The digital biomarker assessments consist of the following:

- 1) Caregivers and participants will be asked to complete daily reported outcome measures ('surveys') in the smartphone app. Caregivers will be asked a small number of questions each day relating to RRBs, social interactions and symptoms associated with autism. Depending on the participant's ability, the participant will also be asked the same set of questions. Participant ability and specific symptoms will be assessed by the clinician at the screening visit and the app will be configured accordingly.
- 2) Participants will be assessed with performance outcome measures that will be within the smartphone app ('active tests'). Each active test will be a simple task in the app that lasts 1 to 4 minutes. The tests will assess spatial working memory, emotion recognition, social cooperation and the participant's speech. During the tests, touch interactions will be captured by the smartphone. Audio will be recorded during the speech test. Once a week caregivers will also be asked to record a conversation with the participant that is at least 5 minutes long. Additional people may join this recording, provided they are formally informed by the caregiver. The ability of the participant to complete the active tests will be assessed by the clinician at the screening visit.

The participant and caregiver will receive daily reminders to complete the surveys and frequent reminders to perform active tests.

3) For passive monitoring, the participant will be asked to wear a wrist-worn wearable each day during all waking hours. At their convenience, participants are also encouraged to wear the wearable at night. This device will track the participant's body movements. It may track heart rate. For location tracking, the participant will also be asked to carry the smartphone. Caregivers may be given small transmitters to be placed around the home to facilitate in home location tracking. Participants are asked to charge the devices overnight.

For privacy reasons, no participant-identifying information is recorded. In addition, participants are able to pause the location recording. For the conversation recording, after completing a conversation recording it is possible to delete some or all of that recording.

All data will be transferred to the Sponsor. If participants have a Wi-Fi network at home, they are encouraged to connect their smartphone to enable data transfer. If no Wi-Fi network is available, the sensor data will be transferred during site visits or after the devices have been returned. Data are encrypted and uploaded to secure servers whenever the phone is connected to Wi-Fi.

For storage and analysis of audio recordings the Sponsor will follow, in detail, these guidelines: The raw audio data are encrypted in transfer and at rest (industry gold standard 256-bit asymmetric encryption). For data processing and analysis purposes, the raw audio data need to be decrypted. Decryption only occurs on a designated secure Roche server with tight access control. Access is granted to a named list of researchers only. Access will be limited to as few individuals as possible. The amount of raw audio data that is available in a decrypted format on this server is kept to an absolute minimum. To ensure this, decrypted data are either automatically reencrypted or deleted immediately after being processed and analyzed. Analysis of the audio data is automated as far as is possible; manual listening to the raw audio data is kept to an absolute minimum. Manual listening will only be done in selected cases as a quality control step for the automated analysis process.

The devices including detailed instructions and training will be provided to the caregiver at the screening visit. Participants will then have a "run-in" period with the device from the screening visit to the Baseline visit. Participants will be instructed to bring the smartphone and wrist-worn wearable to the Baseline visit and each subsequent clinic visit. They will have the opportunity to ask any questions and adherence and technical status of the device will be checked. Also at scheduled phone contacts (see Table 2) site personal will follow-up on progress in collection of digital biomarker data. At each visit, participants will be asked to conduct the active tests under the supervision of a person trained on the digital biomarker approach.

The smartphone and wrist-worn wearable must be returned to the clinic in cases where the participant does not meet eligibility criteria, at the end of the study and upon early termination.

If any part of the digital biomarker assessments is not suitable for the participant, it will be excluded from the participant's schedule of assessments.

At the end of the study or at the time when the participant has completed the study, *both the* participants *and the caregivers* will be asked to complete satisfaction surveys on their experience using the smartphone during the study.

The pre-configured study smartphone and wrist-worn wearable device will be used for data collection and exploratory assessment only. The smartphone and wearable device will not be used in the diagnosis, cure, mitigation, treatment, or prevention of ASD, and no data (except adherence data) is played back to study participants, caregivers or site staff during the study. As such, the smartphone and wearable device are not considered medical devices in this study.

#### 8.5 TIMING OF STUDY ASSESSMENTS

# 8.5.1 Screening Assessments

Written informed consent for participation in the study must be obtained before performing any study-specific screening tests or evaluations. Informed Consent Forms (ICFs) and assent forms for enrolled participant and for participants who are not subsequently enrolled will be maintained at the study site.

All screening assessments must be completed and reviewed to confirm that participants meet all eligibility criteria. The Investigator will maintain a screening log to record details of all participants screened and to confirm eligibility or record reasons for screening failure

An Eligibility Screening Form (ESF) documenting the Investigator's assessment of each screened participant with regard to the protocol's inclusion and exclusion criteria is to be completed by the Investigator and kept at the investigational site.

Screening assessments will be performed during the time window indicated in the SoA (see Section 1.2), i.e., within 4 to 2 weeks before the Baseline visit. However, in case of unexpected delays due to logistical or technical reasons (e.g., sickness of caregivers or raters), the screening period may be extended to up to 6 weeks.

At screening, tests for illicit drugs and alcohol misuse are at the Investigator's discretion. The Investigator will decide if any tests are required or not to confirm eligibility in context of exclusion criterion #6. In addition, the selection of the appropriate tests and test parameters and the appropriate communication of possible findings to participant and parents according to local regulations will be at the discretion of the Investigator. Roche will support sites in the implementation process should the sites need (e.g., provision of urine dipsticks).

Note: Any positive tests for amphetamines will need to be reviewed carefully by the Investigator on a case by case basis, because a significant proportion of people with ASD are taking stimulants such as methylphenidate for their attention-deficit problems. In such a case of a misleading drug alert, a possible study participant will not be excluded from the study.

# 8.5.2 Assessments during Study and Follow-Up Assessments

All assessments must be performed as per SoA (see Section 1.2). After the study completion/early termination visit, adverse events should be followed as outlined in Sections 8.3.1 and 8.3.3.

# 8.5.3 Assessments at Unscheduled Visits

If a COA (see section 8.1.1) cannot be completed during the visit or for a scale the total score (e.g., the composite scores for Vineland™-II) cannot be calculated with the available data, it should be tried to repeat the scale during an unscheduled visit within up to approximately 2 weeks.

Please see Section 1.2 for activities that are required to be performed in case of an unscheduled visit.

# 9. STATISTICAL CONSIDERATIONS

### 9.1 SAMPLE SIZE JUSTIFICATION

Approximately 90 participants with ASD will be enrolled into six cohorts with approximately 15 participants each by two factors IQ and age:

- IQ: participants with ABIQ  $\geq$  70 vs participants with (ABIQ  $\geq$  50 and < 70)
- Age: children 5 to 12 years; adolescents 13 to 17 years and adults 18 to 45 years

In addition, 45 TD healthy participants (15 children age 5 to 12 years, 15 adolescents age 13 to 17 years, and 15 adults age 18 to 45 years) will be enrolled for validation of digital biomarkers only.

The sample size was determined by practical considerations and not based on statistical power calculations.

#### 9.2 STATISTICAL ANALYSES

# 9.2.1 Demographics and Baseline Characteristics

Summaries and listings will be prepared for all relevant Baseline characteristics such as IQ, age, sex, ADOS-2, VinelandTM-II, CY-BOCS-ASD, medical history including medications and treatments, caregiver status, educational status of participant and parents, etc.

### 9.2.2 Safety Analyses

All safety analyses will be based on the safety analysis population defined as all participants who signed the ICF.

Table 5 Safety Statistical Analysis Methods

Endpoint	Statistical Analysis Methods
Adverse events	The original terms recorded on the eCRF by the Investigator for adverse events will be coded by the Sponsor.
	Adverse events will be summarized by mapped term and appropriate thesaurus level.

# 9.2.3 Statistical methods for the Primary Objectives

All primary endpoints (RRB scales) will be presented by listings and descriptive summary statistics. Additionally, the following properties will be investigated:

- Test/re-test reliability with methods such as displaying Bland-Altman Plots, and calculating intra-class correlation coefficients (ICC) using the Baseline and 2-weeks data by means of an ANOVA model with fixed visit effects.
- Internal consistency with methods such as determining Cronbach's alpha.
- Correlating the Baseline values with the corresponding 12-weeks values.

The structure of missing data and drop outs will be investigated (this will also apply for the secondary and exploratory endpoints).

# 9.2.4 Statistical methods for the Secondary Objectives

The effect of age and IQ on RRBs in subjects with ASD will be evaluated with graphical displays and by applying regression models with the RRB scale as dependent and age and IQ and other possible covariates

The correlation structure between scales will be evaluated by means of multivariate methods such as principal component analyses and factor analyses

All listed p-values will be interpreted only as descriptive weights and not in a confirmatory sense.

Further details of planned analyses will be provided in the technical document.

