# 8.1.1.3 Administration of both the Caregiver and Participant-reported Scale Version "if deemed appropriate by Investigator"

For adolescents and adults both versions of the Routine Inventories and the Repetitive Behavior Questionnaires scale should be administered in individual participants at the same visit if the Investigator deems the non-mandatory version of the scale appropriate (see Table 4 and Sections 8.1.1.10 and 8.1.1.11). This includes the participant-reported adult versions (RBQ-2A and ARI) and the caregiver-completed pediatric versions (RBQ-2 and CRI-R).

- For adolescent participants the caregiver-completed RBQ-2 and CRI-R are mandatory scales. The participant-reported versions RBQ-2A and ARI will be completed as well, if deemed appropriate, and if the Investigator deems the participant able to complete these scales based on mental age.
- For adult participants the self-reported versions RBQ-2A and ARI are mandatory scales.
   The caregiver-reported RBQ-2 and CRI-R will be completed as well, if deemed appropriate by Investigator.

Similarly, and "if deemed appropriate by Investigator," the caregiver will complete the CSHQ for adult participants- Adolescent participants will complete the participant-reported PSQI and BAI (see Table 4).

If an adult participant is unable to complete a self-reported adult scale (e.g., because of mental age or other reasons) the corresponding caregiver-reported scale version will be used if it is deemed appropriate by Investigator and if such a scale version exists (i.e., RBQ-2 is to be completed if RBQ-2A is skipped, CRI-R if ARI is skipped, CSHQ if PSQI is skipped).

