# 8.1.1.10 Repetitive Behavior Questionnaire (RBQ-2)

The RBQ-2 is a 20 items questionnaire to assess the spectrum of RRBs observed in individuals with ASD such as repetitive motor movements, rigidity/adherence to routine, preoccupation with restricted patterns of interest and unusual sensory Interest (Leekman et al 2007; Honey et al 2012). The RBQ-2 exists in two different versions, a caregiver-reported version for pediatric subjects RBQ-2 and a participant-reported version for adults RBQ-2A (Barrett et al 2015).

It will take the caregiver approximately 20-30 minutes to complete the pediatric version of the RBQ-2.

F. Hoffmann-La Roche Ltd 46/Protocol BP40331, Version 2 For the adult self-administered version of the RBQ-2A the adult participant will need 20-30 minutes to complete.

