# 8.1.1.11 Childhood Routines Inventory- Revised (CRI-R) and Adult Routines Inventory (ARI)

The CRI-R (for children and adolescents) and ARI (for adults) were developed together and are closely related scales (Evans et al 2017). The CRI-R and ARI questionnaires capture a wide range of RRBs, including stereotypies, tics, compulsions, habits, sensory sensitivities, and focused interests, in the context of typical and atypical development in children, adolescents and adults across the entire lifespan. All items will be answered on a five-point Likert scale from not at all/ never, a little/ rarely, somewhat/ sometimes, quite a lot/ often, and very much / always.

The caregiver-completed CRI-R scale for pediatric subjects includes 62 items. It will take the caregiver about 17 minutes to complete the CRI-R.

The participant-reported ARI scale for adult subjects includes 55 items and will be completed by the participant. It will take the participant about 17 minutes to complete the ARI.

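### Does the change from caregiver to self-report questionnaires at age 18 leave the age analysis of RBQ-2 and CRI-R/ARI in need of a new rule?

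*Combined protocol and SAP*

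**What the plan says.** The effect of age and IQ on RRB is a secondary objective (Section 3, Table 3). Section 9.2.4 will address it with graphs and by "applying regression models with the RRB scale as dependent and age and IQ and other possible covariates". It names no questionnaire version and no informant, and it adds: "Further details of planned analyses will be provided in the technical document". The same section limits p-values to a descriptive role.

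Section 8.1.1.3 fixes which version is given. "For adolescent participants the caregiver-completed RBQ-2 and CRI-R are mandatory scales"; Table 4 gives the same forms for children. "For adult participants the self-reported versions RBQ-2A and ARI are mandatory scales". In adolescents and adults the other version is added at the same visit "if the Investigator deems the non-mandatory version of the scale appropriate", which for adolescents depends on mental age. Sections 8.1.1.2 and 8.1.1.3 add a substitution rule: an adult who cannot complete the self-report form skips it, and the caregiver form may take its place at the Investigator's discretion.

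On the instruments, Section 8.1.1.10 states "The RBQ-2 exists in two different versions", one for caregivers and one for self-report. Section 8.1.1.11 states "The caregiver-completed CRI-R scale for pediatric subjects includes 62 items" and "The participant-reported ARI scale for adult subjects includes 55 items".

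**The concern.** For these two measures, form and informant both change at exactly the age that separates adolescents from adults. If RBQ-2 were put into one regression with RBQ-2A, or CRI-R with ARI, a jump at 18 could be reported as an effect of age when it came from the questionnaire or from who answered it. For CRI-R and ARI the raw totals are not even on one metric, since one has 62 items and the other 55. Section 9.2.4 does not say which version is the dependent variable, so at first sight the plan allows this.

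At stake would be the reading of a secondary objective on two of five RRB measures (counting each pair as one, beside CY-BOCS-ASD, MERS-R and RBS-R), in a study meant to guide the choice of scales for later drug trials.

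**Working it through.** **The plan's own figure.** Section 9.1 gives six cohorts of about 15: 6 × 15 = 90, so 30 per age group and 15 per ABIQ stratum within each. This reproduces. There is no power calculation to check.

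**Is the contrast at 18 aliased?** Take a design matrix for these 90 with columns for intercept, adolescent, adult and ABIQ stratum. Its rank is 4 of 4. Add an indicator for the mandatory self-report form: the rank stays 4, now of 5 columns. The adult column and the form column are identical. So on mandatory forms the contrast of adults with younger participants cannot be separated from form and informant.

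**What remains with age as a continuous variable?** The documents give no age distribution or residual variance. Assume 30 per group, ages uniform within each group, a linear age effect and equal residual variance. With bands 5–<13, 13–<18 and 18–<46:

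- band means: 9, 15.5, 32
- within-band variances (width²/12): 5.33, 2.08, 65.33
- variance of age in all 90: 117.97
- variance of age in the 60 participants aged 5–17: 14.27

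The standard error of the age slope, relative to one form in all 90, is √[(90 × 117.97)/(n × variance used)].

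| Data used | Calculation | SE ratio |
|---|---|---|
| Caregiver form, 5–17 | √[10,617/(60 × 14.27)] | 3.52 |
| Self-report form, 18–45 | √[10,617/(30 × 65.33)] | 2.33 |
| Both, with a version term | within-form variance (60 × 14.27 + 30 × 65.33)/90 = 31.29; √(117.97/31.29) | 1.94 |

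If all adults were 18–30, total variance would be 47.56, adult variance 14.08, and the ratios 2.24, 3.18 and 1.83. The last row in each case also assumes the same slope below and above 18. These ratios describe a narrower age range and fewer participants. The comparator, one form in all 90, is not on offer for age-specific questionnaires.

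**What if a form shift were ignored?** The documents give no informant effect, so this is illustration only. With no true age effect, 30 adults against 60 younger participants and SD 1, the chance of p < 0.05 is Φ(d/√(1/30 + 1/60) − 1.96). For an assumed shift d of 0.2, 0.5 or 0.8 SD it is 0.14, 0.61 or 0.95. It applies only if the versions are merged with no version term.

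**Does the plan merge them?** No section says so, and several points run the other way.

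- Section 8.1.1.3 treats each version as a mandatory scale in its own right, and Section 8.1.1.11 describes CRI-R and ARI as related but separate scales.
- Section 9.2.3 calls for Cronbach's alpha, and Table 3 for the factor structure of each scale. Both need one fixed set of items. A set of 62 and a set of 55 cannot share them, so CRI-R and ARI must be handled separately before any regression is run.
- The wording of Section 9.2.4 allows further covariates and sends the detail to the technical document.

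**Which scale covers 5–45 without a switch?** The RBS-R is mandatory and caregiver-completed at all ages (Table 4, Section 8.1.1.9). CY-BOCS-ASD and MERS-R also keep one form, but their raters draw on participant and caregiver (Section 8.1.1.6), and for MERS-R on others too (Section 8.1.1.8), so the mix of sources may vary with age.

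**The case for a change.** The best case for a change is that the aliasing is exact, that a version covariate repairs it only by assuming one slope on both sides of 18, and that one sentence would close the question at no cost. The versions given together do not fully solve it. They are chosen by the Investigator, partly on mental age, which is plausibly tied to the other regressor, IQ. The number who will complete both is unknown, and Section 9.2.4 plans no use of them.

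The substitution rule adds to this. Planned allocation is balanced, with 15 and 15 by ABIQ in each age group, so the switch at 18 alone does not confound IQ. But adults who cannot self-report may contribute only the caregiver form. Form can then be linked to IQ among adults, and adult self-report data may lose those of lower ability. Moving adults to the caregiver form makes the contrast estimable, but weakly. If 1, 5 or 15 of 30 adults (assumed counts) were analysed on it, the standard error of the adult–child contrast would be 1.02, 0.50 or 0.34 SD, against 0.26 with no form term.

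All of this stands as a limit on what these two measures can say about age across 18. It does not show that the planned analysis is wrong. The limit would stay whatever Section 9.2.4 said, because it lies in instruments made for different ages. Removing it would mean giving the caregiver forms to every adult. By Table 4 that is at most 20–30 plus about 17 minutes, so 37–47 minutes each and 18.5–23.5 caregiver hours for 30 adults at one visit. These forms are described as pediatric, and the plan reasonably leaves their use in adults to the Investigator.

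**Conclusion.** The observation is correct, but it is a gap that analysts fill sensibly. On mandatory forms, age across 18 cannot be told apart from form and informant for RBQ-2/RBQ-2A and CRI-R/ARI. The natural reading of Section 9.2.4 is one model per scale, which already avoids the error: age within 5–17 on the caregiver form and within 18–45 on the self-report form. The cost is precision, with age-slope standard errors roughly 2.2 to 3.5 times those of one form in all 90. That rests on the assumed uniform ages, linear age effect and equal residual variance. No bias can be sized, because the documents give no informant effect and propose no pooling.

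Consequences are small: the objective is secondary, p-values are descriptive, and the RBS-R spans 5–45 with one form and one type of informant. When the results are read, a step at 18 on these two measures should not be taken as an age effect. The adult self-report sample should be treated as at most about 30 and possibly depleted at lower ability. Those are matters for ordinary analysis and reporting, and no change to the plan is needed.
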